1.7 Risk/Benefit Assessment

1.7.1 Known Potential Risks

High-dose radiation has been known to cause toxicity to normal tissue. This is manifested variably depending on the area of the body treated. While the potential toxicities can be serious and include death, these toxicities are rare when high-quality, high-dose radiation is delivered within established normal tissue dose constraints using appropriate immobilization, image guidance, and institutional experience. We have successfully tested many Lattice SBRT plans prescribed to 66.7 Gy in 5 fractions using institutional quality assurance protocols similar to conventional SBRT. Therefore, we expect the toxicity risks associated with Lattice SBRT plans to be similar to conventional SBRT if the required established dose constraints are met.

Blood collection prior to and after radiotherapy poses a small risk of pain and bleeding.

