11.6 Continuous Toxicity Monitoring using Pocock-type boundary

The toxicities will be reviewed and monitored on a continuous basis. Early stopping of this trial will be based on the excessive Lattice SBRT treatment emergent severe adverse events (TEAE) of grade 3 or higher non-hematological rate. We assume the TEAE rate is expected ~30% and a toxicity rate of 40% or more is not desired. Sequential boundaries will be used to monitor dose-limiting toxicity rate after three patients are enrolled and evaluable for toxicity. The accrual will be halted if excessive numbers of TEAE are seen, that is, if the number of TEAE is equal to or exceeds b_n out of n patients with full follow-up (see table below). This is a Pocock-type stopping boundary that yields the probability of crossing the boundary at most 0.3 when the rate of TEAE is equal to the acceptable rate of 0.3 (Ivanova, Qaqish, and Schell 2005).

| | | | | | | | | | | | | |
|--------------------|---|---|---|---|---|---|----|----|----|----|----|----|
| number of patients | 4 | 5 | 6 | 7 | 8 | 9 | 10 | 11 | 12 | 13 | 14 | 15 |
|--------------------|---|---|---|---|---|---|----|----|----|----|----|----|

| | | | | | | | | | | | |
|---------------|---|---|---|---|---|---|---|---|---|---|---|
| Boundary (bn) | 4 | 5 | 5 | 6 | 6 | 7 | 7 | 8 | 8 | 9 | 9 |
|---------------|---|---|---|---|---|---|---|---|---|---|---|

Thus, based on the continuous monitoring algorithm for toxicity using Pocock-type boundary, the study will halt if excessive Lattice SBRT -related adverse events occur in the 4 of the first 4 patients, or 6 of the first 8, or 7 of the first 11, or 9 of the 20 patients has completed the trial.

The operating characteristics including early stopping probability, expected number of TEAEs and associated with the calculated boundaries are listed below.

| TEAE rate | Early stopping (hitting the boundary) probability | Expected number of TEAEs | Standard deviation on number of TEAEs | Expected number of patients enrolled | Standard deviation of number of patients enrolled | Expected TEAE rate | Standard deviation on TEAE rate |
|------------------|--|---------------------------------|--|---|--|---------------------------|--|
| 0.30 | 0.0447 | 4.41 | 1.65 | 14.71 | 1.50 | 0.31 | 0.15 |
| 0.40 | 0.1707 | 5.58 | 1.54 | 13.96 | 2.65 | 0.43 | 0.18 |
| 0.50 | 0.4101 | 6.24 | 1.38 | 12.49 | 3.67 | 0.55 | 0.19 |

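### Section 11.6 gives 0.3 as the level of its stopping boundary, but the tabulated boundary is a 0.05-level one for 15 patients, and its halt probabilities depend on a maximum sample size the documents do not settle

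*Combined protocol and SAP*

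**What the plan says.** Section 11.6 sets the reference rates: "We assume the TEAE rate is expected ~30% and a toxicity rate of 40% or more is not desired". Accrual halts "if the number of TEAE is equal to or exceeds b_n out of n patients with full follow-up". Monitoring begins once three patients are evaluable, and the boundary table starts at four. The level is given in one sentence: the boundary "yields the probability of crossing the boundary at most 0.3 when the rate of TEAE is equal to the acceptable rate of 0.3".

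The boundary table has columns from 4 to 15 patients. The text below it names halts at 4 of 4, 6 of 8, 7 of 11 and 9 of 20. The operating-characteristics table follows, and its first row begins "0.30 | 0.0447 | 4.41", the second figure being the early-stopping probability. The rows for 40% and 50% give 0.1707 and 0.4101.

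Planned enrolment is 20 in sections 11.1, 11.4 and 11.5, and 10 in the synopsis and section 4.5.

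**The concern.** In a Pocock-type design, the crossing probability at the acceptable rate is the number from which the whole boundary is built. The sentence puts it at 0.3 and the table at 0.0447, about 6.7 times smaller (0.30 / 0.0447). The likeliest cause is that the toxicity rate of 0.3 was repeated where the error level belongs.

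Two things are at stake. A reader who takes the sentence as the design level would think the trial accepts a substantial risk of a false halt in return for early detection, whereas the tabulated rule does the reverse. And anyone who regenerates the boundary from the stated level, for example when the sample size is reconciled, would obtain a materially different halting rule. Safety is the primary objective, and this is the only numerical trial-level toxicity halt in the protocol.

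**Working it through.** **Inputs (all from 11.6).** Acceptable rate 0.30; undesired rate 0.40 or more; halt when the event count reaches b_n; columns n = 4 to 15; the printed boundary row; the printed operating characteristics.

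**1. The boundary row.** The text as read shows "Boundary (bn) | 4 | 5 | 5 | 6 | 6 | 7 | 7 | 8 | 8 | 9 | 9", which is 11 values for 12 columns. One value may have been lost in reading the PDF, so I do not count this as a defect. Restoring a third 6 among n = 7 to 9 gives 4, 5, 5, 6, 6, 6, 7, 7, 8, 8, 9, 9 for n = 4 to 15. That fits the text's 4 of 4, 6 of 8 and 7 of 11.

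**2. Reproducing the printed table.** Let f_n(k) be the probability of k events in n patients without an earlier crossing. Then f_n(k) = (1 − p) f_{n−1}(k) + p f_{n−1}(k − 1), and mass at k ≥ b_n is removed and added to the crossing probability. With a maximum of 15:

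| True rate | Crossing, computed | Crossing, printed | Expected patients, computed | Expected patients, printed |
|---|---|---|---|---|
| 0.30 | 0.0447 | 0.0447 | 14.71 | 14.71 |
| 0.40 | 0.1707 | 0.1707 | 13.96 | 13.96 |
| 0.50 | 0.4101 | 0.4101 | 12.49 | 12.49 |
| 0.60 | 0.6957 | 0.6957 | 10.40 | 10.40 |

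The remaining four rows also match. Aligning the 11 values simply left or right gives 0.0280 or 0.0610 at 30%, which does not reproduce the table and is nowhere near 0.3.

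**3. The level of this boundary.** A Pocock-type boundary takes b_n as the smallest k with P(Bin(n, 0.3) ≥ k) ≤ c, with the same c at every n. The reconstructed row follows from c = P(Bin(9, 0.3) ≥ 6) = 0.0253. For example:
- n = 4: 4 of 4 has tail 0.3^4 = 0.0081 (≤ c); 3 of 4 has 0.0837 (> c).
- n = 11: 7 has tail 0.0216 (≤ c); 6 has 0.0782 (> c).

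The next looser cut-off is 0.3^3 = 0.0270, which adds a halt at 3 of 3 and gives total crossing 0.0591. If looks start at n = 4, it is P(Bin(7, 0.3) ≥ 5) = 0.0288, with total crossing 0.0517. Both exceed 0.05. So only a nominal level from 0.0447 to just below 0.0517 (or 0.0591) yields the printed boundary. That interval contains 0.05 and excludes 0.3.

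**4. A boundary built at 0.3.** With N = 15 and looks from n = 4, the largest usable cut-off is c = P(Bin(8, 0.3) ≥ 4) = 0.1941. The boundary is 3, 3, 4, 4, 4, 5, 5, 6, 6, 6, 7, 7, and it crosses with probability 0.2988, 0.5756 and 0.8152 at 30%, 40% and 50%. At 40% the printed rule is 0.1707 / 0.5756 = 0.30 times as likely to halt.

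**5. Dependence on the maximum n.**

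| Rule | 30% | 40% | 50% |
|---|---|---|---|
| Table, accrual ends at 10 | 0.0319 | 0.1133 | 0.2734 |
| Table, accrual ends at 15 | 0.0447 | 0.1707 | 0.4101 |
| Table plus 9 of 20 | 0.1259 | 0.4208 | 0.7581 |

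A boundary regenerated at 0.05 for N = 20 ends at 11 of 20, not 9, and crosses with probability 0.0489, 0.2109 and 0.5144. Nine is the table's entry at n = 15. Section 11.4's 99.53% is also a 15-patient figure: 1 − 0.7^15 = 0.9953, whereas 1 − 0.7^20 = 0.9992. Both suggest that the calculations were made for 15 patients.

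**6. What not crossing would show.** For the 15-patient table, not crossing has probability 1 − 0.0447 = 0.9553 at 30% and 1 − 0.1707 = 0.8293 at 40%, a ratio of 1.15. With 9 of 20 added, the ratio is 0.8741 / 0.5792 = 1.51. Either way it barely separates the two rates.

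**The case against.** Several points on the other side stand.

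- **The sentence is not false.** A probability of 0.0447 is indeed no more than 0.3. This is a misdescribed design level, not an arithmetic impossibility. The 0.05 is printed nowhere; it is inferred, although the match is exact.
- **Nothing is concealed.** A reader might infer that the misstated level hides the rule's weakness from the oversight bodies. The documents do not support that: the true halt probabilities are tabulated in the same section, and the operative b_n values do not depend on the sentence.
- **17% is not a fixed property of the trial.** A reader might conclude that the study simply runs on 83% of the time at a 40% rate. That holds only for a 15-patient maximum. With the 9-of-20 halt it runs uncrossed about 58% of the time (1 − 0.4208), although the added crossings come after patient 15 and so protect less.
- **Low power is partly unavoidable.** Separating 40% from 30% with 10 to 20 patients is hard under any rule, and tolerating that is a design choice.
- **The plan does not claim that not crossing proves safety.** No section says it shows a rate below 40%. The caution is worth adding, but it does not correct a stated claim.
- **Other oversight exists.** Section 10 provides ongoing monitoring and semi-annual reports, and section 5.9 allows the cancer center to close the study.

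None of this removes the mismatch between the stated level and the boundary printed beneath it.

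**Conclusion.** The point holds as a misstated design level. The sentence in 11.6 implies a 0.3-level boundary, while the one tabulated is the 0.05-level boundary for 15 patients. The difference is material: 4 of 4 against 3 of 4 at the first look, and a halt probability of 0.17 against 0.58 at the rate of which the plan says "a toxicity rate of 40% or more is not desired".

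The protection actually offered cannot be given as one number until the maximum n is settled. At a 40% rate it ranges from 0.11 (10 patients) through 0.17 (15) to 0.42 (20 with the 9-of-20 halt). In the last case crossing at 30% is 0.126, so a level of 0.05 would not describe the rule either.

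These results assume independent patients with a common event rate, looks after every patient from the fourth, and the reconstructed boundary row, which is supported by its exact reproduction of all eight printed rows.

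**What to change.** 1. Reconcile the maximum n across the synopsis and section 4.5 (10), the table in 11.6 (15) and sections 11.1, 11.4 and 11.5 (20). Decide whether the 9-of-20 checkpoint belongs to the rule; at present it is in the text but not in the table.
2. Replace the 0.3 with the level actually used, stated together with that n. It is 0.05 if the tabulated 15-patient boundary is kept. Changing the sentence to 0.05 while keeping 20 patients and 9 of 20 would introduce a new error.
3. Regenerate the boundary and operating characteristics for the settled n. If 0.3 was truly intended, regenerate both at that level instead.
4. State the resulting halt probabilities at 40% and 50%, and add that completing accrual without crossing is weak evidence against a 40% rate.

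The cost is one corrected sentence and a regenerated table, after the sample-size reconciliation that the protocol needs in any case. No extra patients are required.

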1.6.2 Scientific Rationale for Study Design

Tumor burden incurs significant morbidity in terms of symptomatology, including pain, dyspnea, hemoptysis, and mass effect on surrounding organs. Palliative hypofractionated radiotherapy is known to be a useful modality for control and/or amelioration of such symptoms. However, large tumors are difficult to treat with traditional palliative methods. Hypofractionated radiotherapy may offer insufficient control and SBRT may be associated with a high rate of toxicity.

Dose escalation using SFRT may offer improved local control, symptom relief, and reduced toxicity compared with traditional radiotherapy methods. Also, SFRT has been associated with significant activation of systemic anti-tumor cytokines and chemokines. Since Lattice SBRT has not been tested, the goal of this study is to evaluate the safety of this approach.

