4.5 Strategies for Recruitment and Retention

Our institution sees a high volume of patients that are referred for palliative radiotherapy.

The primary source of patients who are eligible for this study will be radiation oncologists within our department. The most likely service lines to see patients with large tumors in need of palliative radiotherapy are sarcoma, thorax (i.e. lung cancer), gastrointestinal, gynecologic, palliative, and head and neck. [name] (service line chief of sarcoma) is the PI, and the other service line chiefs are enthusiastic about this trial and are listed as co-investigators: [name] (Thorax), [name] (Gastrointestinal), [name] (Gynecologic), [name] (Palliative), and [name] (Head and Neck). Additionally, a full-time research coordinator will be assigned to this study who will be screening all patients who are referred to our department for palliative radiotherapy.

With the current rate of patients in need of palliative radiotherapy presenting to our department, we anticipate approximately 125 patients per year will be eligible for this protocol. A conservative estimate is that 20% of these patients will consent to participate in this study. This yields an estimated accrual of 25 patients per year. We anticipate that we will enroll 10 patients of all genders, races, and ethnicities. Given the hypofractionated course of therapy, 90% of patients should be able to complete therapy. We anticipate that we will accrue approximately 1-2 patients per month, therefore completing accrual in 6 months. Patients will be accrued from the outpatient clinics and inpatient hospitals of one U.S. site. Potential participants will be identified by our multidisciplinary team physicians and discussed in tumor board.

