7.1 WU PI Reporting Requirements

7.1.1 Reporting to the Human Research Protection Office (HRPO) at Washington University

Reporting will be conducted in accordance with Washington University IRB Policies.

Pre-approval of all protocol exceptions must be obtained prior to implementing the change.

7.1.2 Reporting to the Quality Assurance and Safety Monitoring Committee (QASMC) at Washington University

The PI is required to notify the QASMC of any unanticipated problems involving risks to participants or others occurring at WU or any BJH or SLCH institution that has been reported to and acknowledged by HRPO. (Unanticipated problems reported to HRPO and withdrawn during the review process need not be reported to QASMC.)

QASMC must be notified within **10 days** of receipt of IRB acknowledgment via email to [contact]. Submission to QASMC must include the myIRB form and any supporting documentation sent with the form.

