10.0 DATA AND SAFETY MONITORING

In compliance with the Washington University Institutional Data and Safety Monitoring Plan, the Principal Investigator will provide a Data and Safety Monitoring (DSM) report to the Washington University Quality Assurance and Safety Monitoring Committee (QASMC) semi-annually beginning six months after accrual has opened (if at least one patient has been enrolled) or one year after accrual has opened (if no patients have been enrolled at the six-month mark).

The Principal Investigator will review all patient data at least every six months, and provide a semi-annual report to the QASMC. This report will include:

- HRPO protocol number, protocol title, Principal Investigator name, data coordinator name, regulatory coordinator name, and statistician
- Date of initial HRPO approval, date of most recent consent HRPO approval/revision, date of HRPO expiration, date of most recent QA audit, study status, and phase of study
- History of study including summary of substantive amendments; summary of accrual suspensions including start/stop dates and reason; and summary of protocol exceptions, error, or breach of confidentiality including start/stop dates and reason
- Study-wide target accrual
- Protocol activation date
- Average rate of accrual observed in year 1, year 2, and subsequent years
- Expected accrual end date
- Objectives of protocol with supporting data and list the number of participants who have met each objective
- Measures of efficacy (phase I studies only if efficacy is objective of the protocol)
- Measures of efficacy
- Early stopping rules with supporting data and list the number of participants who have met the early stopping rules
- Summary of toxicities
- Abstract submissions/publications
- Summary of any recent literature that may affect the safety or ethics of the study

The study principal investigator and Research Patient Coordinator will monitor for serious toxicities on an ongoing basis. Once the principal investigator or Research Patient Coordinator becomes aware of an adverse event, the AE will be reported to the HRPO and QASMC according to institutional guidelines.

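### The only halting rule counts a treatment-related death as one grade 3 event and needs at least four affected patients; no route in the plan requires accrual to pause after such a death

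*Combined protocol and SAP*

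**What the plan says.** **Halting rule (11.6).** Stopping is driven by "treatment emergent severe adverse events (TEAE) of grade 3 or higher non-hematological rate". Accrual halts "if the number of TEAE is equal to or exceeds b_n out of n patients with full follow-up". The earliest condition is that "the study will halt if excessive Lattice SBRT -related adverse events occur in the 4 of the first 4 patients"; the text then gives 6 of 8, 7 of 11 and 9 of 20. Grade 5 has no threshold of its own here or anywhere else in the document.

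**Novelty and known risk.** Section 1.6.2 gives the reason for the study as "Since Lattice SBRT has not been tested". Section 1.7.1 says "While the potential toxicities can be serious and include death", and adds that such toxicities are rare when dose constraints and technique are respected.

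**Routes to oversight.**
- Section 10.0: the PI and research coordinator watch for serious toxicities continuously, and AEs they learn of go to HRPO and QASMC under institutional guidelines. The document does not give those timelines.
- Section 7.1.2: "The PI is required to notify the QASMC of any unanticipated problems" that HRPO has acknowledged, within 10 days of that acknowledgment.
- Appendix C: an unanticipated problem that results in a participant's death goes to HRPO within 1 working day. AEs and SAEs that need no expedited report go to QASMC in the six-monthly toxicity table.
- Section 10.0: routine reports to QASMC are due "semi-annually beginning six months after accrual has opened", provided at least one patient is enrolled.

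**Accrual.** The synopsis plans ten patients, and 4.5 expects 1 to 2 per month, "therefore completing accrual in 6 months". Sections 11.1, 11.4 and 11.5 plan 20 patients. Section 11.5 expects about 1 per month and also 10 to 12 months in total.

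**The concern.** The concern is limited to deaths attributed to Lattice SBRT. Deaths from progression are recorded separately (9.1) and are not at issue.

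The boundary is built around an expected 30% rate of grade 3 or higher events. A rule with that tolerance is far too permissive for fatal toxicity, where one or two events in a small trial would normally lead someone to look before the next patient is enrolled. If the pooled count is the only thing that can halt accrual, the protocol can be followed to the letter while several patients die of the treatment. Safety is the sole primary objective, so this scenario should be settled in advance and not left to the discretion of those running the trial.

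**Working it through.** **1. Reproduce the plan's own figure.** As it reads in the document, the boundary row has 11 values for 12 sample sizes (4 to 15), so one value must be restored. This may be an extraction effect and is not counted as an error. Let the cumulative count grow by 1 with probability p per patient, and stop when it reaches b_n. With b_4 to b_15 = 4, 5, 5, 6, 6, 6, 7, 7, 8, 8, 9, 9 and a maximum of 15 patients, the exact crossing probability is 0.0447 at p = 0.30, 0.1707 at 0.40 and 0.4101 at 0.50. These match the printed table, as do its other five rows. This reconstructed boundary is used below.

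**2. How many treatment-related deaths fit under the rule?** With no boundary crossed, the largest possible counts are:

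| Patients | Deaths possible without a halt |
|---|---|
| 3 | 3 (no boundary before n = 4) |
| 4 | 3 |
| 10 | 6 |
| 15 | 8 |
| 20 (text rule, 9 of 20) | 8 |

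**3. How likely are repeated deaths?** The documents give no fatal-toxicity rate, so q = 5% and 10% are assumptions. P(≥2) = 1 − (1−q)^n − n·q·(1−q)^(n−1).

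- n = 10, q = 5%: 1 − 0.599 − 0.315 = 0.086
- n = 10, q = 10%: 1 − 0.349 − 0.387 = 0.264
- n = 20, q = 5%: 1 − 0.358 − 0.377 ≈ 0.264
- n = 20, q = 10%: 1 − 0.122 − 0.270 = 0.608

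**4. Would deaths trip the boundary?** Putting p = q into the recursion of step 1 gives 0.00001 (0.001%) at 5% and 0.00019 (0.02%) at 10%. This counts deaths alone and ignores grade 3 and 4 events, which also add to the count.

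**5. Allowing for other events.** Suppose the first three patients all die of treatment and later patients have any qualifying event at the plan's 30%. Patient 4 then brings a halt with probability 0.30, and the cumulative chance by patient 15 is 0.47. So even then the trial is more likely than not to run to 15 patients without crossing.

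**6. When does QASMC first look routinely?**

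| Plan | Enrolled at six months |
|---|---|
| 10 patients in 6 months (synopsis, 4.5) | 10 of 10 |
| 20 in 10 months (11.5) | 20 × 6/10 = 12 of 20 |
| 20 in 12 months (11.5) | 20 × 6/12 = 10 of 20 |
| 20 at 1 per month (11.5) | 6 of 20 |

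**7. Follow-up lag.** The rule counts patients with full follow-up, which is about 14 + 90 = 104 days. With 10 patients evenly spaced over about 182 days (one every 18.2), the fourth enters near day 55 and completes near day 159, when nine are enrolled. Section 5.6 ends evaluation at death, so a patient who dies may count sooner; 11.6 does not say.

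**The case against.** The strongest reply is that the boundary is not the only safeguard. The PI and coordinator monitor continuously. Section 10.0 sends AEs to HRPO and QASMC under institutional guidelines, and that route is not confined to unanticipated problems. An unanticipated fatal problem reaches HRPO within 1 working day and QASMC soon after. A pooled grade 3 or higher count also matches the primary endpoint.

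Much of this stands, and it rules out several readings that a reader might infer:

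- **That QASMC hears promptly only of unanticipated problems.** The documents do not show this. The institutional guidelines are not reproduced and may set a short deadline for deaths.
- **That a treatment-related death would escape expedited reporting because 1.7.1 names death as a risk.** That is possible but not established. Section 1.7.1 also calls such toxicities rare, and Appendix B leaves expectedness to outside guidance. The fair statement is that a death might not be classed as unanticipated.
- **That the first routine QASMC report always arrives after accrual is over.** This is true only of the 10-patient, 6-month plan.
- **That 0.02% is the chance of the trial halting when 10% of patients die of treatment.** It is not, because grade 3 and 4 events also count. At overall event rates of 30% and 40% the plan's own table gives 4.5% and 17%.
- **That these patients have an adequate standard alternative.** Section 1.5 names a standard regimen but doubts its durability in large tumors, and section 2.0 says effective options are lacking. The point does not depend on this.

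What the reply does not supply is an obligation. Each route concerns who is told. None makes accrual wait, or requires QASMC to review a treatment-related death before the next patient is enrolled.

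**Conclusion.** The point holds in a limited form. The sole halting rule gives a treatment-related death the weight of one grade 3 event and cannot fire on fewer than four affected patients. Up to 6 such deaths in 10 patients, or 8 in 20, are compatible with it. At assumed fatal-toxicity rates of 5% and 10%, two or more deaths would occur with probability 9% and 26% with 10 patients, and 26% and 61% with 20. Deaths alone would almost never cross the boundary.

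The probabilities rest on the assumed death rates. The crossing figures also rest on a reconstructed boundary, which reproduces every printed stopping probability. The counts in step 2 need no assumed rate; the entry for three patients needs only the 4-of-4 starting point.

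This is a gap in what the protocol obliges. It is not evidence that a death would go unnoticed or that the investigators would fail to act. It is worth closing because the approach is described as untested and the remedy is cheap. The size of the timing problem cannot be settled until the 10-patient and 20-patient plans are reconciled.

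**What to change.** 1. **Section 11.6:** add a trial-level trigger, separate from b_n. A grade 5 event attributed to Lattice SBRT suspends new accrual pending QASMC review. Limit it to attributed events, so that the progression deaths recorded as grade 5 under 9.1 do not set it off.
2. **Section 10.0 and Appendix C:** state that such an event, or a boundary crossing, is reported to HRPO and QASMC within a stated number of working days, whether or not it is judged unanticipated.
3. **Synopsis, 4.5 and 11.1 to 11.5:** reconcile sample size and accrual period, so that the position of the six-month report relative to accrual is known.

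The first two changes cost a few sentences and one table row. The downside is a possible short accrual pause after a single death. The boundary and its operating characteristics are unchanged, because the trigger sits alongside b_n.

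### Section 11.6 does not give one usable stopping rule: its operating characteristics are for 15 patients, its restated rule runs to 20, and its boundary row appears one value short

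*Combined protocol and SAP*

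**What the plan says.** All of the following is in section 11.6 unless another place is named.

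- **Rates.** "We assume the TEAE rate is expected ~30% and a toxicity rate of 40% or more is not desired".
- **Rule.** Accrual halts "if the number of TEAE is equal to or exceeds b_n out of n patients with full follow-up", with a pointer to the table. Monitoring begins after three patients: "Sequential boundaries will be used to monitor dose-limiting toxicity rate after three patients are enrolled and evaluable for toxicity".
- **Table.** The patient counts are "4 | 5 | 6 | 7 | 8 | 9 | 10 | 11 | 12 | 13 | 14 | 15", which is 12 columns. The limits are "Boundary (bn) | 4 | 5 | 5 | 6 | 6 | 7 | 7 | 8 | 8 | 9 | 9", which is 11 values.
- **Restatement.** The study halts if events "occur in the 4 of the first 4 patients, or 6 of the first 8, or 7 of the first 11", with a last point of 9 among 20.
- **Operating characteristics.** The first row begins "0.30 | 0.0447 | 4.41 | 1.65 | 14.71": rate, halting probability, mean and SD of events, mean number enrolled. The halting probabilities at 40, 50, 60 and 70% are 0.1707, 0.4101, 0.6957 and 0.9052.
- **Claimed property.** The boundary "yields the probability of crossing the boundary at most 0.3 when the rate of TEAE is equal to the acceptable rate of 0.3".
- **Sample size.** Sections 11.1, 11.4 and 11.5 plan 20 patients; the synopsis and section 4.5 plan 10. Section 11.4 gives 99.53% as the chance of seeing at least one toxicity in 20 patients at a 30% rate.

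**The concern.** This is the protocol's only numerical halting rule, and the semi-annual safety report in section 10.0 must give the early stopping rules with supporting data, so staff have to apply it. The table, the sentence under it and the operating characteristics ought to be three views of one rule. As they stand, the table and operating characteristics end at 15 patients, the sentence ends at 20, and the row has fewer limits than columns. Read from the left, the row also gives a limit of 8 at n = 11, where the sentence gives 7.

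Two things are at stake. Staff could not say with confidence whether a given count halts accrual. And the halting probabilities that a safety committee would rely on may belong to a different rule or a different trial size.

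**Working it through.** **Method.** Let f_n(k) be the probability that k of the first n patients have an event and no limit has been reached. At true rate p,

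f_n(k) = (1 − p) f_{n−1}(k) + p f_{n−1}(k − 1).

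At each n with a limit, the probability on k ≥ b_n is removed and added to the halting probability. E(N) is the sum, over n from 0 to the maximum minus 1, of the probability of not having halted by n.

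**Step 1: reproduce the plan's figures.** I took every boundary on n = 4 to 15 that starts at 4 of 4 and rises by 0 or 1 per patient (2^11 = 2,048 boundaries). Exactly one gives 0.0447 at 30% and 0.4101 at 50%:

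4, 5, 5, 6, 6, 6, 7, 7, 8, 8, 9, 9.

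It also gives 0.1707, 0.6957 and 0.9052 at 40, 60 and 70%, and E(N) of 14.71/13.96/12.49/10.40/8.18 at 30 to 70%, all as printed.

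**Step 2: confirm the maximum of 15 without the search.** With a halting probability of 0.0447 at 30%, 95.53% of trials run to full size. A 20-patient maximum would then need E(N) of at least 0.9553 × 20 = 19.1. The printed value is 14.71.

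**Step 3: the figure in section 11.4.** P(at least one event) = 1 − 0.7^n.

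- n = 10: 97.18%
- n = 15: 1 − 0.00475 = 99.53%
- n = 20: 1 − 0.00080 = 99.92%

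The 99.53% is the 15-patient value.

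**Step 4: the row as it reads.** Set from the left, the 11 values differ from the Step 1 boundary at n = 9 (7 against 6), n = 11 (8 against 7), n = 13 (9 against 8) and n = 15 (none against 9). Set from the right, they give no limit at n = 4 and contradict 4 of the first 4. Adding one 6 gives the Step 1 boundary.

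**Step 5: the sentence.** The points 4/4, 6/8 and 7/11 agree with the Step 1 boundary; 9 among 20 lies outside the table. Over 20 patients it makes no difference whether each limit is checked only at its named count or applied as soon as that many events occur, because event counts never fall. Within the first 15 patients I applied each limit as soon as its count was reached.

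| Halting probability (%) at true rate | 30% | 40% | 50% | 60% |
|---|---|---|---|---|
| Stated | 4.5 | 17.1 | 41.0 | 69.6 |
| Step 1 boundary, 15 patients | 4.5 | 17.1 | 41.0 | 69.6 |
| Row set from the left, none at 15 | 2.8 | 11.4 | 30.2 | 57.5 |
| Row set from the right, none at 4 | 6.1 | 19.9 | 44.0 | 71.6 |
| Sentence as printed, over 20 | 12.1 | 41.5 | 75.5 | 94.5 |
| Sentence, within the first 15 | 3.5 | 14.7 | 37.7 | 67.0 |

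A check on the fifth line: at 30%, the last point alone, P(9 or more of 20), is 11.3%, already well above 4.5%.

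**The case against.** The strongest reply is that there is only one boundary. The rule refers to the table, so the table governs; the sentence picks out some of its points; and one extra 6 reconciles the row, the sentence at 4, 8 and 11, and the operating characteristics. A repeated digit is easily lost when a PDF table is converted to text.

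Much of this stands. A reader might infer that the plan contains three rival boundaries, but the sentence's first three points match the operating characteristics exactly. A reader might also infer that the sponsor left out a value; that cannot be said until the original page is checked.

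A further tempting inference is that the printed rules halt later and less often than stated. The documents do not support that in general. It is true of the row set from the left, and of the sentence within 15 patients. It is false of the row set from the right, and false of the sentence over the 20 patients it names, where a limit is hit far more often than stated.

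The reply does not reach the mismatch in size. The sentence is running text, not a broken table, and it names 20 patients. Restoring the missing 6 completes the row only to n = 15. The cap of 0.3 on the crossing probability does not help either: 0.0447 satisfies it, but so does 12.1%, so it cannot show which rule was meant.

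**Conclusion.** Wrong as written. Section 11.6 does not give one rule that matches its stated operating characteristics and the planned sample size.

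- **Firm, whatever the row shows on the original page.** The operating characteristics and the 99.53% belong to a 15-patient design, while section 11 plans 20 and the synopsis 10. Patients 16 to 20 have no table limit. The stated probabilities do not describe the sentence: at a 40% true rate, which the plan calls undesirable, 17.1% is stated, against 41.5% over 20 patients and 14.7% within the first 15.
- **Conditional.** If the row really has 11 values on the page, it cannot be applied as printed. Read from the left, it halts in 30.2% at a 50% rate against 41.0% stated. If the missing 6 is there, this part falls away.

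No single direction of error should be claimed; it depends on how the row is aligned and over how many patients the sentence is applied. The calculations assume independent patients with a common event rate and limits checked after each patient. The uniqueness of the Step 1 boundary is among boundaries that start at 4 of 4 and rise by at most one per patient.

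**What to change.** 1. Check the boundary row on the original page.
2. State one maximum sample size and use it in the synopsis, section 4.5 and sections 11.1, 11.4, 11.5 and 11.6.
3. Print a complete boundary row up to that maximum, with one limit under every patient count.
4. Make the restating sentence agree with that row, or delete it and let the table govern.
5. Recompute the operating characteristics and the 99.53% for that maximum.

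If the maximum is 15, the 12 values 4,5,5,6,6,6,7,7,8,8,9,9 match the sponsor's own printed figures, and those figures and the 99.53% stay. Completing the row to 15 while keeping 20 patients would not be enough, because patients 16 to 20 would still have no limit.

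The cost is a text amendment and a short recalculation. If the maximum is not 15, the stated halting probabilities will change. As an illustration only, carrying a limit of 9 forward from n = 15 to n = 20 would give 12.6/42.1/75.8/94.6% at rates of 30/40/50/60%.
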